One potential pitfall of association studies in population-based samples is false-positive signals resulting from population stratification. We will use an Illumina panel of 278 ancestry informative markers from the HumanHap 550K chip (Illumina; San Diego, CA) to account for potential effects of population stratification in our analyses either by adjusting the variance of the statistic or by adjusting the populations (88, 89). We attempt to eliminate false positives by assigning higher priority to signals that are replicated in multiple populations either at the same SNP, same haplotype block or same gene. We recognize that these methods represent global adjustments based on genome-wide averages of admixture, thus do not provide information about the chromosomal region containing SNPs of interest. However, newer methods are beginning to appear that attempt to define the ancestral blocks to potentially allow for local admixture adjustment in case-control analyses (90). We plan to evaluate new methods as they become available and integrate those that will add power to our analyses.

c. *Power calculation for the candidate gene analyses*

We estimated the effect sizes we could reasonably expect to detect at 80% power in these three samples. The calculations were made across a range of allele frequencies, and for sample sizes of 75, 97, and 585, in the current study, TRIPOD, and the Diabetes Prevention Program (DPP), respectively. For purposes of these calculations, we further assumed a dominant genetic model in which mean TZD response levels were to be compared between two genotype groups (e.g., AA vs. Aa/aa). The effect sizes are parameterized to reflect the difference between the group means, expressed in terms of the

standard deviation units. By convention, differences between groups of 0.8 SD, 0.5 SD and 0.2 SD are considered large, medium, and small effects, respectively.

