For the current study ($n = 75$ subjects) and TRIPOD studies ($n = 97$ subjects), we would have 80% or higher power to detect medium size effects (0.7 SD unit differences between means) across a wide range of allele frequencies (i.e., minor allele frequencies 0.1-0.5). For a putative subgroup of the current study with $n=38$, we would have 80% or higher power to detect large effect sizes (1.0-1.2) across the same allele frequencies. For the DPP ($n = 597$ subjects), we would have 80% or higher power to detect small size effects (0.3 SD unit differences between means) also across a wide range of allele frequencies. It is also worth noting that subjects to be recruited from this study will have mRNA levels measured, a very proximal phenotype that can be used as an additional outcome for the genetic association studies. One might expect a very large effect of an associated SNP on this particular phenotype.

E. HUMAN SUBJECTS RESEARCH

Protection of Human Subjects

1. Risks to the Subjects

a. Human subjects involvement and characteristics

Inclusion criteria

- Male or female who self-identifies as (in NIH classification terms) White.
- Age 35 - 65 years
- BMI 25 - 40 kg/m²

The age and BMI criteria were chosen to favor subjects with a relatively high likelihood of having insulin resistance and chronic inflammation, which makes intervention clinically meaningful.

Exclusion criteria

- History of diabetes (Doctor told pt. they had diabetes or pt. is taking diabetes medication)
- Fasting glucose value diagnostic for diabetes
- 2-h oral glucose tolerance test diagnostic for diabetes
- Medications that the investigator judges will make interpretation of the results difficult or increase the risk of participation (e.g., anticoagulants)
- Disease that the investigator judges will make interpretation of the results difficult or increase the risk of participation (e.g., anemia, cardiac decompensation, intolerance to rosiglitazone, lidocaine or other agents used)
- Pregnancy
- Physical dimensions exceeding the limits of any equipment used

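### The candidate-gene power statement calls 0.3 SD small and 0.7 SD medium, although the plan sets these at 0.2 and 0.5 SD, where power is below 80%

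*Combined protocol and SAP*

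**What the plan says.** All the relevant text is in Section D.4.c (Power calculation for the candidate gene analyses).

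- Aim of the calculation: "We estimated the effect sizes we could reasonably expect to detect at 80% power in these three samples".
- Samples: "for sample sizes of 75, 97, and 585, in the current study, TRIPOD, and the Diabetes Prevention Program (DPP), respectively". The result sentence for the DPP uses 597 instead of 585.
- Model: "we further assumed a dominant genetic model in which mean TZD response levels were to be compared between two genotype groups", with the effect being the difference in means in SD units.
- Scale: "By convention, differences between groups of 0.8 SD, 0.5 SD and 0.2 SD are considered large, medium, and small effects, respectively".
- Result for the current study and TRIPOD: "we would have 80% or higher power to detect medium size effects (0.7 SD unit differences between means"), for MAF from 0.1 to 0.5.
- Result for the DPP: "we would have 80% or higher power to detect small size effects (0.3 SD unit differences between means"), again over a wide range of allele frequencies.

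Neither the significance level nor the sidedness is stated for this calculation. Section D.1 concedes that the 75 subjects have little power for the effect of individual variants on clinical response, and turns to the DPP and TRIPOD for that purpose.

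**The concern.** The scale and the results stand in adjacent paragraphs and do not agree. The effect called small for the DPP is one and a half times the plan's small effect (0.3/0.2 = 1.5). The effect called medium for n=75 and n=97 lies 0.1 SD from the plan's large effect and 0.2 SD from its medium one. Both labels make the samples sound more sensitive than they are.

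This matters most for the DPP, the largest of the three cohorts and one of the two to which Section D.1 turns for power. A colleague who carries away the words rather than the bracketed values would credit the DPP with 80% power at 0.2 SD, and the two smaller samples with 80% power at 0.5 SD.

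**Working it through.** **Inputs from Section D.4.c.** N = 75, 97, and 585 or 597; dominant two-group comparison; MAF q from 0.1 to 0.5; scale 0.2/0.5/0.8 SD; target 80%.

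**Assumptions of this check.** Hardy-Weinberg proportions, a single test, and alpha 0.05, two-sided first and then one-sided, because the plan states neither.

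**Formula.** The carrier share is f = 1 - (1 - q)². The two-group t test has N - 2 degrees of freedom and noncentrality d × √(N f (1 - f)). At q = 0.1, f = 0.19 and f(1 - f) = 0.1539. At q = 0.3, f = 0.51 and f(1 - f) = 0.2499, almost the maximum of 0.25. At q = 0.5, f = 0.75 and f(1 - f) = 0.1875. Over the stated range, power is therefore lowest at q = 0.1 and highest near q = 0.3.

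**Step 1: the plan's own figures (two-sided 0.05).**

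| Sample | d (SD) | MAF 0.1 | MAF 0.3 | MAF 0.5 |
|---|---|---|---|---|
| DPP, 585 | 0.3 | 81.1% | 95.2% | 88.0% |
| DPP, 597 | 0.3 | 81.9% | 95.5% | 88.7% |
| TRIPOD, 97 | 0.7 | 76.3% | 92.7% | 84.0% |
| Current study, 75 | 0.7 | 65.1% | 84.9% | 73.6% |

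The DPP statement reproduces with either N. TRIPOD falls short only at the lower edge, reaching 80% from MAF of about 0.11. The n=75 statement holds only for MAF of about 0.18 to 0.43. One-sided, n=75 still has only 76% at MAF 0.1.

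**Step 2: power at the plan's own small and medium.** Noncentrality at q = 0.1 and q = 0.3:

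- DPP, N = 597, d = 0.2: 0.2 × √(597 × 0.1539) = 1.917 and 0.2 × √(597 × 0.2499) = 2.443.
- N = 75, d = 0.5: 0.5 × √(75 × 0.1539) = 1.699 and 0.5 × √(75 × 0.2499) = 2.165.
- N = 97, d = 0.5: 0.5 × √(97 × 0.1539) = 1.932 and 0.5 × √(97 × 0.2499) = 2.462.

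| Sample | d (SD) | Two-sided 0.05, range over MAF 0.1-0.5 | One-sided 0.05 |
|---|---|---|---|
| DPP, 585 | 0.2 | 47.4-67.5% | 60-78% |
| DPP, 597 | 0.2 | 48.2-68.4% | 61-79% |
| Current study, 75 | 0.5 | 38.8-57.0% | 52-69% |
| TRIPOD, 97 | 0.5 | 48.1-68.3% | 61-79% |

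No allele frequency reaches 80% in any row. Even an exact 50/50 split gives at most 68%, 57% and 68% two-sided for the DPP, n=75 and n=97.

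**Step 3: difference detectable with 80% power, two-sided 0.05, over MAF 0.1-0.5.** DPP about 0.23-0.30 SD; TRIPOD about 0.58-0.73 SD; n=75 about 0.66-0.84 SD. As a rough check, the normal approximation for n=75 at MAF 0.1 is (1.96 + 0.84)/√(75 × 0.1539) = 2.80/3.397 = 0.82, and the t test raises it slightly to 0.84.

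**The case against.** The SD value is printed beside each label, so nobody is denied the number. At that number the DPP sentence is correct, and 0.3 is nearer 0.2 than 0.5. The same paragraph calls 1.0-1.2 SD large for a subgroup of 38, which suggests that the words are used as rough categories. If they were bands (0.2-0.5 small, 0.5-0.8 medium), 0.3 and 0.7 would both fit. For the 75 subjects, Section D.1 already gives the caution.

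Much of this stands. It removes any charge of miscalculation against the DPP sentence and makes *medium* for 0.7 SD the weaker of the two labels. It does not remove the mismatch: the plan gives three point values and no bands. Even read as bands, the lower end of the DPP's small band, including 0.2 SD itself, falls below 80%.

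A reader might go further and infer that a null DPP result is meant to rule out small genotype effects. The documents do not say so. Aim 3 is a search for associations, Section D.4.b gives priority to replicated signals, and no decision rule, futility criterion or sample size depends on the word *small*.

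**Conclusion.** The point holds as a labelling fault that overstates sensitivity. On the plan's own scale, and assuming a single two-sided 0.05 test under the dominant model with MAF 0.1-0.5, power is 47-68% for a small effect in the DPP. For a medium effect it is 39-57% in the 75 subjects and 48-68% in TRIPOD. The percentages depend on the assumed alpha; the conclusion that they are below 80% also holds at one-sided 0.05, and any allowance for multiple SNPs would lower them.

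It would be wrong to infer that the DPP calculation is in error, since it reproduces at 0.3 SD. The one stated figure that clearly does not hold over its stated range is 80% at 0.7 SD for n=75; for n=97 the two-sided shortfall is marginal and confined to MAF near 0.1. All figures here concern the dominant model that the plan used for power. Section D.4 makes per-allele coding the primary analysis, and no power is given for that.

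**What to change.** In Section D.4.c:

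1. Drop the words *small* and *medium* from the two result sentences.
2. State the difference detectable with 80% power over MAF 0.1-0.5: about 0.23-0.30 SD for the DPP, 0.58-0.73 SD for TRIPOD and 0.66-0.84 SD for n=75 (single two-sided 0.05 test).
3. Add the power at 0.2 SD for the DPP and at 0.5 SD for n=75 and n=97.
4. Do not keep the 80% claim at 0.7 SD for n=75 across the whole MAF range. Relabelling 0.7 SD alone would leave that claim standing. For n=97, note the shortfall near MAF 0.1.
5. State the alpha and sidedness used, recomputing items 2-4 if they differ from two-sided 0.05.
6. Use one DPP sample size throughout, 585 or 597.

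The cost is a few lines of text and less favourable stated figures. Recruitment, conduct and analysis are unchanged.

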correlated to TZD response will be defined as candidate genes and will be pursued using state-of-the-art molecular genetic approaches to define all common sequence variation and haplotype structure of the gene. We will then genotype these SNPs in our subjects to determine if these SNPs or haplotypes associate with TZD response. Although the 75 subjects we plan to recruit for this study will provide very rich phenotype and microarray information for defining TZD response and for selecting candidate genes to study, they will not be particularly powerful to discern the effect of specific gene variants on clinical response to TZDs.

However, they may be useful in discerning associations of gene variants with mRNA levels encoded by that gene (or within the same regulatory pathway). Thus, in the next stage of our study, we will take advantage of established collaborations with investigators of large prospective studies which involved a TZD intervention and for which relevant response traits have been collected, the DPP Study, and the TRIPOD Study (now continued as PIPOD).

[figure not shown]

Fig. 9. Timeline of the study

High throughput genotyping of 1536 SNPs in 100 candidate genes will be performed in these cohorts and association of SNPs and haplotypes with TZD response will be examined. It is our hope that in a subset of these 100 candidate genes we will find consistent evidence for a role in TZD response, e.g., altered mRNA levels in those with the variant SNP/haplotype and association with TZD response in both populations.

2. **Specific Aim 1. Defining interindividual variability in TZD response**

a. *Subject recruitment and screening*

Seventy-five subjects will be recruited for this study from the following sources:

- A large database belonging to the Division comprising over 500 subjects recruited at health fairs. These subjects have provided basic health information, given blood for genotyping, and indicated that we may contact them to inform them about future genetic studies. Additionally, some subjects have had oral glucose tests. We have previously successfully recruited subjects from this collection. This collection will also allow rapid identification of potential volunteers for our study if the focus should later change to a particular genotype or clinical profile.

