Statistical approach. To study the gene expression profiles that are related to the 3-month rosiglitazone intervention, we will compare the expression profile of the muscle (and fat) tissues from pretreatment subjects to that from post-treatment subjects. We will calculate and normalize gene expression levels by the Robust Multichip Average method (RMA) (37) and quantile normalization (11). The statistical significance of these comparisons will be assessed using LIMMA package software (27) (a linear model approach implemented in Bioconductor) or non-parametric methods (e.g., Kruskal-Wallis- or Mann-Whitney U-tests), using SAS software. A critical issue in microarray analysis is to avoid a high "false discovery rate" (9) (FDR; the probability that a gene is incorrectly identified as differentially expressed), due to the large number of genes compared. We will consider genes to be differentially expressed only if they meet criterion values for fold-change and p-value (for example, >1.5 and <0.05, respectively). For each analysis of differential expression, we will experiment with different combinations of criterion values and calculate the resultant FDR (using MULTTEST package in Bioconductor (61)) for each set of criteria, until we obtain acceptable stringency for fold-change, statistical significance and FDR (we anticipate using conservative FDRs in the range of 1-5%).

To study the association between these differentially expressed (DE) genes and the response of the primary and secondary traits to TZDs, for each DE gene, we will generate linear regression models using the change in the response of the primary (i.e., insulin sensitivity) and secondary responses to TZDs as dependent variables and the gene expression change in response of the treatment and demographic and clinical measures as the independent variables. For the regression models, we will report the adjusted squared correlation coefficient (R^2_{adj}), which corrects for the degrees of freedom. The association between each DE gene and each trait in response to TZDs can be measured by the adjusted squared correlation coefficient. The overall association with primary and secondary traits can be based on the score that is calculated as the weighted sum of the corresponding the adjusted squared correlation coefficients. The weights can be determined by principal component analysis. The importance of each gene can be determined by its score.

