validation. We will choose validated SNPs from the multiple public databases (e.g., dbSNP, CELERA, Hap-Map) as well as from SNPs that have already been converted into Illumina assays for their linkage and fine mapping panels (http://www.illumina.com/snp_linkage.htm). SNPs that appear independently in more than one database or SNPs that have been experimentally validated and have allele frequencies greater than 5%. As these databases become more complete (the next version of dbSNP will have >10 million SNPs; [name], personal communication), we expect to be able to obtain the great majority of SNPs that we will initially genotype from these databases. In genes that do not have adequate sequence variant information from these sources (i.e., less than a 1 SNP per 3-5 kb density), we will perform DNA sequence analysis to identify new SNPs. The regions of greatest interest will be potentially functional regions, including exons, exon-intron junctions, regulatory regions, and other intragenic regions that are phylogenically conserved. These regions and other regions in which the inter-marker distance exceeds 5 kb will be sequenced in 10 European Caucasians and 10 African Americans (40 alleles). This number of subjects will provide >87% power to detect gene variants with an allele frequency of 10% or greater. When considering the density of SNPs within candidate genes, we will also take into account what is known about the haplotype structure of the gene/region based upon information from Hap-Map and other sources. Indeed, [name], consultant on this proposal, is a member of the Hap-Map project and will be able to provide expert advice regarding SNP selection.

b. Specific Aim 2b

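### The SNP–mRNA outcome is not specified; if it is unmasked array level, SNPs under array probes (or in LD with them) can give false associations

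*Combined protocol and SAP*

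**What the plan says.** Section D.1 concedes that the 75 subjects have limited power for clinical associations but adds that "they may be useful in discerning associations of gene variants with mRNA levels encoded by that gene (or within the same regulatory pathway". It then gives an example of consistent evidence for a gene: "altered mRNA levels in those with the variant SNP/haplotype and association with TZD response in both populations". Section D.4.c returns to the idea: "subjects to be recruited from this study will have mRNA levels measured, a very proximal phenotype that can be used as an additional outcome", and "One might expect a very large effect of an associated SNP on this particular phenotype".

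On measurement, section D.2.f (Statistical approach) states "We will calculate and normalize gene expression levels by the Robust Multichip Average method", followed by quantile normalization. Q-RT-PCR on the same RNA is planned to confirm and quantify regulated genes (D.1; D.2.f, Quantitative Real time-PCR) and contributes to choosing the 100 candidates (end of the GenMAPP paragraph in D.2.f). On SNPs, section D.3.a says "The regions of greatest interest will be potentially functional regions, including exons, exon-intron junctions, regulatory regions" and other conserved intragenic sequence.

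The only quality control stated before the association analysis (D.4) concerns genotypes: duplicate samples and Hardy-Weinberg tests. Nothing compares SNP positions with probe positions.

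**The concern.** Oligonucleotide arrays read mRNA by hybridization to short probes matched to the transcript. This is general technical knowledge, not something the documents state. A variant inside a probe's target can weaken binding, so carriers show a lower signal at the same mRNA level. Tested against that SNP, or one correlated with it, the result looks like an effect of the SNP on its own gene.

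Three features of the plan let this pass unnoticed:

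- SNPs are sought in exons, among other regions.
- The Q-RT-PCR step confirms pre/post differences. A gene can be truly TZD-regulated, pass that step, and still show a false genotype difference in array level.
- Section D.3.b drops SNPs in high LD with others (the example is r² above 0.7). The SNP under the probe may therefore go untyped while its tag, possibly a regulatory one, carries the signal. Hypothesis 3 puts its emphasis on regulatory variants.

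Replication helps little here, because the plan describes mRNA measurement only in the 75. Fat and muscle are run on the same kind of array, so the same mismatch could recur in both tissues and look like corroboration.

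**Working it through.** **1. The plan's own figure.** The plan gives no effect size or error rate for the SNP–mRNA test. The only n=75 figure in D.4.c is at least 80% power for a 0.7 SD difference, dominant model, minor allele frequency (MAF) q = 0.1–0.5. Assuming a two-sided 5% test, power = Φ(d√(N·c(1−c)) − 1.96), with carrier share c = 1−(1−q)².

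- q=0.3: c=0.51, √(75×0.51×0.49)=4.33, 0.7×4.33=3.03, Φ(1.07)=86%.
- q=0.1: c=0.19, √(75×0.19×0.81)=3.40, 0.7×3.40=2.38, Φ(0.42)=66%.
- q=0.2 and 0.4: 83%. q=0.5: 75%.

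The figure holds for q=0.2–0.4 but not at the two ends. That is a separate matter, and it depends on the assumed alpha.

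**2. Inputs for the probe question.** From the documents: n=75, RMA summary, additive 0/1/2 coding (the primary genetic model in D.4). Assumed, because the documents give none of them: 11 probes per probe set, probe noise SD 0.25 log2, between-person SD 0.15–0.30 log2, MAF 0.2–0.4, loss of 0.5–1.0 log2 per variant allele in each affected probe, no true mRNA effect.

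**3. Method.** Simulate genotype and an 11-probe matrix for 75 people, lower the affected probes by the loss times allele count, summarise by median polish (as RMA does), regress on allele count, and record the share with p<0.05. There were 400 data sets per setting in the underlying calculation.

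| Affected probes | False positives, array level | Spurious shift per allele |
|---|---|---|
| 0 | about 5% | none |
| 1 | 7–20% | about 0.1–0.2 SD |
| 2 | 19–68% | about 0.2–0.5 SD |
| 3 | 35–98% | about 0.33–0.76 SD |

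**4. Hand check.** For a shift of b SD per allele, let k = b√(N·2q(1−q)). The rejection rate is about Φ(k−1.96)+Φ(−k−1.96).

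- One probe, b=0.1, q=0.2: k=0.1×√(75×0.32)=0.49, rate 8%.
- One probe, b=0.2, q=0.4: k=0.2×√(75×0.48)=1.20, rate 22%.
- Two probes, b=0.2, q=0.2: k=0.98, rate 17%.
- Two probes, b=0.5, q=0.2: k=2.45, rate 69%.

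These agree with the simulated ranges.

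**5. Pre/post change.** If an affected probe loses δg at both visits, then (post−δg)−(pre−δg) = post−pre, and the loss cancels on the log scale. Simulated false positives for change: 3–8%.

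**6. Other assumptions.** With 8, 11 or 16 probes, MAF 0.3, between-person SD 0.4 log2 and 1 or 3 log2 lost over two alleles, level gives 7–14% with one affected probe, 6–45% with two and 80–100% with about half. Change gives 3–8%, or 3–10% if affected probes also lose half of the true change. A PCR-like level untouched by the SNP gives 2–7%.

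**The case against.** The case against giving this much weight is substantial.

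- **Platform.** D.1 and D.4.c do not name one. Elsewhere mRNA levels are sometimes determined by PCR (the Q-RT-PCR paragraph of C.4; the TNFα and IL6 assays in D.2.f), and the 100 genes should have PCR data because PCR validation feeds their selection. A reader might infer that array signal is the planned outcome. The documents do not say so, although D.1 credits the 75 with microarray information just before raising the mRNA idea, and RMA is the only array summary described.
- **Level or change.** Aim 1c works with change, where the artefact largely cancels. Only a level analysis is exposed. Level is the word used in D.1 and D.4.c, but no such analysis is specified.
- **Reach.** A reader might infer that exonic SNPs in general will show false mRNA differences. Only SNPs under a probe, or in LD with one, can do so; exons are one of several target regions, and the affected share cannot be derived from the documents.
- **Size.** It is tempting to equate the artefact with the very large effect that D.4.c anticipates. With one or two affected probes the shift is about 0.1–0.5 SD per allele, at most about medium on D.4.c's own scale, so that reading fails in the usual case.
- **Consequence.** D.1 joins altered mRNA to clinical association in both populations, and D.4.b gives priority to replicated signals.

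All of this stands and limits the point. It does not remove it: no sentence restricts the SNP–mRNA test to PCR or to change, and none screens probes against SNPs.

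**Conclusion.** The concern holds in a conditional form. The plan allows a same-gene SNP–mRNA test whose outcome is undefined. Under one permitted choice, RMA array level without masking, the test is biased for SNPs under probes or in LD with them. The inflation is modest with one affected probe (about 7–20% at a nominal 5%) and larger with two or more; pre/post log change stays near nominal. These rates rest on assumed probe counts, noise, allele frequencies and signal loss, and the number of genes affected is unknown.

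The artefact cannot produce clinical association in DPP or TRIPOD, and it does not affect choosing the 100 genes on pre/post change. What it can do is strengthen the wrong SNP and point to a false regulatory mechanism. The planned Q-RT-PCR would not catch this as written, because it confirms pre/post differences and not genotype differences. This is a secondary analysis, but the remedy is cheap enough to adopt.

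**What to change.** State in D.4 which measurement (array or Q-RT-PCR) and which form (level or pre/post log change) the SNP–mRNA tests will use. Then add:

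1. Before any SNP–mRNA test on array level, list the array probes for the 100 genes that overlap a SNP known from Aim 2 sequencing or from the databases. Drop those probes and recompute RMA for the affected probe sets.
2. Count a SNP–mRNA association as supporting evidence only if it holds on the masked probe set, or by Q-RT-PCR with primers and probe placed off known SNPs.

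The cost is a few lines of code and a short addition to the analysis plan; the SNP positions are already being collected. Expression will be slightly noisier for probe sets that lose probes, and a few may become unusable for this secondary analysis. Masking covers only known SNPs.
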